4.4 Criteria for dropout

Patients who are unable to complete the 3-month follow-up due to subjective or objective reasons.

4.5 Privacy protection

Patients' medical records (study case records/CRFs, laboratory reports, etc.) will be securely stored at the hospital, with clinical test results well documented. Only the researchers involved in this study, the ethics committee, and regulatory authorities will be permitted to access the patient's medical records. Any public reports on the study findings will not disclose any patient identifying information. We will make every effort, within the bounds of the law, to protect the privacy of patients' medical data. In accordance with medical research ethics, except for personal privacy information, trial data will be accessible for public inquiry and sharing, limited to web-based electronic databases.

5. Sample size calculation

Based on published literature and clinical experience, the estimated 90-day functional independence rate (defined as mRS ≤ 2) in the control group is 35%. Using a two-tailed significance level of $\alpha = 0.05$, with 80% statistical power ($1-\beta = 0.8$), and a 1:1 allocation ratio between the experimental and control groups, we estimate that 376 participants per group are needed to detect a 10% improvement in the functional independence rate between groups. Considering a 20% dropout rate, a total of 910 subjects are needed to be enrolled, with 455 participants in each group.

Randomization will be performed using block randomization with block size of 10 (with at least 10 participants per center). For practical implementation, each center will be allocated a block, for example, if Center 1 plans to enroll 20 participants, blocks 1-2 will be allocated. This randomization scheme will be followed accordingly. If stratification variables are used, randomization will be performed within each stratum.

6. Randomization

Patients will be randomly assigned to two groups in a 1:1 ratio. Stratified block randomization will be used, with stratification by study center and intravenous thrombolysis. A 1:1 randomization

sequence will be generated. The randomization process will be managed using the "Jinling mouse" app.

7. Medication protocol

Blood pressure will be continuously monitored using a noninvasive device applied to the nonparalyzed arm or the right arm. The measurement intervals are as follows: every 15 minutes within the first hour post-randomization, every hour from 2 to 6 hours, every 6 hours from 4 to 24 hours, and then twice daily until day 7 (if the patient is discharged or dies before day 7, monitoring will be discontinued).

Given the clinical uncertainties regarding the potential benefits and risks, this study encourages adherence to the protocol but allows for adjustments to the treatment plan based on clinical needs. Nicardipine is recommended for blood pressure management, but other antihypertensive medications may be also selected according to the clinician's judgment.

Nicardipine injection administration protocol: dilute with saline or 5% glucose injection to prepare a solution containing 0.01–0.02% nicardipine hydrochloride (0.1–0.2 mg per 1 mL). Administer by intravenous infusion, starting at a rate of 2–10 μ g/kg body weight per minute. Once the target blood pressure is achieved, adjust the infusion rate while continuously monitoring blood pressure. If necessary, intravenous administration can be increased to a dose of 10–30 μ g/kg body weight per minute.

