9.1 Statistical analysis populations

Intention-to-Treat (ITT) Population: This population will include all randomized patients, regardless of whether they receive the intended intervention. A modified ITT analysis will be conducted based on the principle of the closest approach to the ITT population. Patients who withdraw consent before the blood pressure intervention, do not undergo the assigned procedure after randomization, lack endpoint data, refuse follow-up, or are lost to follow-up will be excluded from the statistical analysis. The modified ITT analysis will be used to evaluate the effectiveness and safety of the treatment regimen.

Per-Protocol (PP) Population: This population will exclude all patients with significant protocol violations, such as those who are under 18 years of age, have a final diagnosis other than acute ischemic stroke, have sustained systolic blood pressure <140 mmHg post-surgery, do not achieve reperfusion (mTICI <2b), have a pre-stroke mRS score of 3-5, lack 3-month follow-up data, or do not achieve the expected blood pressure control. The PP analysis will serve as a supplement to the modified ITT analysis.

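### The enrolment target of 910 does not allow for the stated 20% dropout: 376 evaluable per group needs 470 per group (940 in total)

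*Protocol*

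**What the plan says.** Protocol Section 5 (Sample size calculation) assumes a control-group rate of 35% for the primary outcome, 90-day mRS of 2 or less. It sets a two-sided significance level of 0.05, 80% power and "a 1:1 allocation ratio between the experimental and control groups". From these it concludes: "we estimate that 376 participants per group are needed to detect a 10% improvement in the functional independence rate between groups". The enrolment target follows in the next sentence: "Considering a 20% dropout rate, a total of 910 subjects are needed to be enrolled, with 455 participants in each group".

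Two other places determine what dropout does to the analysed number. Section 4.4 defines a dropout as a patient who does not complete the 3-month follow-up, which is when the primary outcome is measured. Section 9.1 describes the modified ITT analysis used to judge effectiveness and safety, and says that patients who "lack endpoint data, refuse follow-up, or are lost to follow-up will be excluded from the statistical analysis".

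**The concern.** An allowance for dropout should ensure that the evaluable number is still there after the assumed loss. The enrolled number must therefore be the evaluable number divided by one minus the dropout rate. The stated 455 per group is too small for that: taking 20% off it does not return 376.

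The main analysis excludes patients without endpoint data, so each such dropout comes directly off the number on which the 80% power was calculated. Ethics committees, sites and readers rely on the enrolment target, and its link to the stated power is broken. The four figures given together (20% dropout, 376 evaluable per group, 80% power, 910 enrolled) cannot all be true.

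**Working it through.** **Inputs, all from Section 5:** control rate 0.35; improvement of 10 percentage points, so 0.45 in the intensive group; two-sided alpha 0.05 (z = 1.96); power 80% (z = 0.8416); 1:1 allocation; dropout 20%; 455 per group enrolled.

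**Step 1: reproduce the 376.** With pooled variance under the null (mean rate 0.40):

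n = [1.96·√(2·0.40·0.60) + 0.8416·√(0.35·0.65 + 0.45·0.55)]² / 0.10²
= [1.96·√0.48 + 0.8416·√0.475]² / 0.01
= 375.6, rounded up to 376.

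This matches the protocol exactly. It also confirms that the 10% improvement is meant as an absolute difference; a relative 10% (35% versus 38.5%) would need 2,978 per group.

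**Step 2: apply the dropout.**

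- Required: 376 / (1 − 0.20) = 470 per group, 940 in total.
- Stated: 455 per group, 910 in total.
- Shortfall: 470 − 455 = 15 per group, 30 in total; 30/940 = 3.2%.

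**Step 3: work back from 455.**

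- Evaluable after 20% dropout: 455 × 0.80 = 364 per group, which is 12 below 376.
- Largest dropout that still leaves 376: 1 − 376/455 = 17.4%.

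**Step 4: power for 35% versus 45%.** Power = Φ{[0.10 − 1.96·√(0.48/n)] / √(0.475/n)}.

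| Evaluable per group | Power |
|---|---|
| 376 | 80.0% |
| 364 | 78.8% |

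With 364 per group, the difference detectable with 80% power from a 35% control rate is 10.16 points, about 10.2.

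**Step 5: does another standard formula rescue 455?**

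| Formula for the evaluable number | Per group | After dividing by 0.80 |
|---|---|---|
| Pooled (or arcsine) | 376 | 470 |
| Unpooled | 373 | 467 |
| Continuity-corrected | 396 | 495 |

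None gives 455. Division by 0.80 yields 455 only from an evaluable number of 364, and the protocol states 376.

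**Possible origin.** Multiplying instead of dividing gives 376 × 1.2 = 451.2, or 452 per group and 904 in total. Rounding 904 up to whole blocks of 10 gives 910. The protocol shows no formula, so this is a conjecture, and the finding does not depend on it.

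**The case against.** The sponsor could fairly make four points.

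- **The effect is slight.** Power falls from 80.0% to 78.8% and the detectable difference rises from 10.0 to 10.2 points. That is small beside the uncertainty in a 35% control rate taken from published literature and clinical experience. This stands: the trial is not seriously underpowered, and the estimand, the test and patient safety are unaffected.
- **The power loss is conditional.** With 455 per group, at least 376 remain evaluable for any dropout up to 17.4%, so 80% power is missed only if losses exceed that. This also stands. But 20% is the protocol's own planning assumption, and the stated power has to be judged under it.
- **Not every dropout need lack an endpoint.** Section 4.4 does not say whether death counts as dropout, and a patient who dies has an mRS of 6. If some of the 20% are deaths, more than 364 per group would be evaluable. That is correct, so 364 is the result when every dropout lacks a 90-day mRS. In the other direction, Section 9.1 also excludes patients who withdraw consent before the intervention or do not receive the assigned procedure. If the 20% covers only incomplete follow-up, these are additional losses.
- **The 20% may have been meant as an addition to the evaluable number.** In that case it is an allowance of about 17% of those enrolled, and the text mislabels it as a dropout rate. The sentence would still need correcting.

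None of these makes 910 consistent with a 20% dropout rate and 376 evaluable per group.

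**Conclusion.** The concern holds. The evaluable number of 376 per group is right; the enrolment target derived from it is not. On the protocol's own figures, 20% dropout requires 940 patients, and 910 is 30 short. If 20% of those enrolled have no 90-day mRS, 364 per group remain, with 78.8% power for 35% versus 45%. This rests on the stated inputs, the pooled-variance formula that reproduces 376, and the exclusion of patients without endpoint data in Section 9.1. It is an isolated arithmetic error with a small effect on power, but it sits in the trial's stated enrolment target and should not be left there.

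**What to change.** Correct the dropout sentence in Section 5 in one of three ways:

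- keep 910 and state that it preserves 376 evaluable per group for dropout up to about 17.4%;
- keep 910 and 20% dropout, and state that the resulting 364 per group give 78.8% power for 35% versus 45%, or 80% power for a difference of about 10.2 points; or
- keep both 20% dropout and 80% power, and change the target to 940 (470 per group).

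Either of the first two is sufficient, and neither needs extra enrolment. The cost is one sentence and a slightly less favourable statement of power or tolerated dropout. The third option costs 30 more patients.

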within 24 hours after successful endovascular therapy) and the standard SBP target group (systolic blood pressure between 130-185 mmHg within 24 hours after successful endovascular therapy). In this study, the difference in blood pressure between the intensified hypotension and standard blood pressure groups was relatively modest (average systolic blood pressure within 24 hours was 128 mmHg and 138 mmHg, respectively), which may have been insufficient to detect the potential benefits of a further reduction in systolic blood pressure. On this basis, the ENCHANTED2/MT study [17] employed a grouping strategy with more pronounced differences in blood pressure and found that, compared to the less intensive treatment group (systolic blood pressure between 140-180 mmHg within 72 hours), the more intensive treatment group (systolic blood pressure <120 mmHg within 72 hours) exhibited a higher proportion of poor functional outcome at 3 months. However, no significant differences were observed between the two groups in terms of symptomatic intracranial hemorrhage or 3-month mortality [17]. The recently published OPTIMAL-BP study [18] reached a conclusion consistent with that of the ENCHANTED2/MT study: the three-month poor functional outcome rate in the intensive management group (systolic blood pressure <140 mmHg within 24 hours) was significantly higher than that in the conventional management group (systolic blood pressure between 140-180 mmHg within 24 hours). Additionally, no significant differences were observed in the incidence of symptomatic intracranial hemorrhage or in the three-month stroke-related mortality between the two groups. The results of the BEST-II study [19], published almost simultaneously, demonstrated that lower SBP targets less than either 140mmHg or 160mmHg after successful endovascular therapy did not meet prespecified criteria for futility compared with an SBP target of 180mmHg or less. Therefore, it cannot be concluded that lower postoperative blood pressure targets are harmful [19]. In summary, existing studies present inconsistent recommendations regarding blood pressure management following successful reperfusion with endovascular thrombectomy, likely due to differences in populations, interventions, and other factors. Further precise researches are necessary to better define the optimal strategy.

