Therefore, we proposed a multicenter randomized controlled trial to investigate the impact of early intensive blood pressure control on the prognosis of patients with embolic stroke after successful reperfusion following endovascular thrombectomy.

2. Objectives

To investigate the safety and efficacy of intensive blood pressure control after successful

reperfusion following thrombectomy in patients with acute anterior circulation large artery embolic stroke.

3. Design

The study employs a multicenter, prospective, randomized, endpoint-blinded, parallel-controlled trial design. Patients with acute anterior circulation large artery occlusive stroke, who receive successful reperfusion after endovascular thrombectomy within 4.5 or 6.0 hours of onset, without significant in-situ or proximal vessel stenosis, and with sustained elevated systolic blood pressure (≥ 140 mmHg for >10 minutes), will be enrolled according to the clinical inclusion and exclusion criteria. The enrolled patients will be randomly assigned to the experimental group or control group (1:1). The experimental group will undergo intensive blood pressure management (target systolic pressure <120 mmHg, achieved and maintained within 1 hour for 48 hours), while the control group will have less intensive blood pressure control (target systolic pressure 140-180 mmHg). Patients will be followed up for 3 months to assess their prognosis.

4. Patient selection

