4.3 Criteria for withdrawal

The study should be terminated if any of the following conditions occur:

Voluntary withdrawal, participants can freely withdraw at any time;

Deliberate or inadvertent non-compliance with the study procedures;

Any other circumstances where the investigator deems that continuing the study would harm the patient's health;

Patients can withdraw from the study at any stage for any reason. Similarly, the investigators have the right to terminate a patient's participation in case of an emergency medical condition. For patients who withdraw, the investigator must inquire about the reason for withdrawal and whether any adverse events (AE) occurred. If the withdrawal is due to an AE, follow-up should be conducted

until the AE is resolved, unless the investigators deem that the condition is due to the patient's underlying disease and is unlikely to resolve. The reason for withdrawal and the date must be recorded in the case report form (CRF).

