13.4 AEs reporting

Any AE occurring during the trial will be reported by the investigators and clinical sites to the relevant national and local regulatory authorities within the specified timeframes, in accordance with national regulations. The investigators will assist the regulatory authorities in investigating the AE and implementing appropriate corrective and preventive measures.

Any SAE occurring during the clinical study must be reported by the investigator to the study's ethics committee and the clinical research sponsor within 24 hours of becoming aware of the event. Additionally, the investigator must complete a serious adverse event form, documenting the time of occurrence, severity, duration, measures taken, and outcome.

The investigators should follow up and record the outcomes of all AEs, tracking patients who withdraw from the study due to an AE until the AE is fully resolved. The investigator must assess whether the AE is related to the study intervention and provide supporting evidence for this assessment. Any clinically significant abnormal findings in clinical or laboratory tests should be recorded on the adverse event form, with follow-up observations at least once a week until the condition normalizes or returns to baseline levels.

Researchers should follow up on all adverse events (AEs) to observe and record their outcomes, and track patients who withdraw from the study due to an AE until it is fully resolved. Researchers must assess whether the AE is related to the research intervention and provide supporting evidence for this assessment. All clinically significant abnormalities in clinical or laboratory tests should be documented in an AE form and monitored during follow-up, with observations conducted at least weekly until normal or baseline levels are restored.

14. Follow-up and medical measures after study completion

The patients will be followed up within 3 months after discharge and continue long-term secondary prevention treatment for cerebral infarction.

15. Data retention

The CRF is prepared in triplicate: one copy is retained by the sponsor, one by the participating institution, and one by the statistical unit. Demographic data, relevant medical history, physical examinations, laboratory test results, concomitant medications, and adverse events are recorded in the CRF as raw data, with any information related to the subject's privacy documented only in the original medical records.

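### The protocol tests a <120 versus 140–180 mmHg contrast that it reports as giving worse function elsewhere, but it states no comparison of the arms for harm during the 910-patient trial

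*Protocol*

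**What the plan says.** **Earlier evidence (Protocol, background before Section 2).** One randomised trial compared <120 mmHg with 140–180 mmHg over 72 hours, and "the more intensive treatment group (systolic blood pressure <120 mmHg within 72 hours) exhibited a higher proportion of poor functional outcome at 3 months". A second trial, of <140 mmHg over 24 hours, is reported as significantly worse on the same outcome. Neither showed a significant difference in symptomatic intracranial hemorrhage (sICH) or in mortality (stroke-related mortality in the second). A third trial found no difference in 3-month outcome. For a fourth, the protocol says harm from lower targets cannot be concluded.

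**This trial (Sections 3, 7.1, 7.2).** The experimental arm has "target systolic pressure <120 mmHg, achieved and maintained within 1 hour for 48 hours"; the control arm has 140–180 mmHg. The background argues that embolic stroke without residual stenosis may respond differently from pooled populations.

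**Size (Section 5).** The independence rate "in the control group is 35"%, and "376 participants per group are needed to detect a 10% improvement in the functional independence rate between groups". After dropout, "a total of 910 subjects are needed to be enrolled, with 455 participants in each group". The test is specified by "Using a two-tailed significance level of" 0.05, and no split across looks is stated.

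**Safety provisions.** Section 4.3 lets a single patient be taken out of the study, for instance under "Any other circumstances where the investigator deems that continuing the study would harm the patient's health". Section 13.4 sends each SAE to the "ethics committee and the clinical research sponsor within 24 hours of becoming aware of the event". sICH and 3-month mortality are primary safety outcomes (8.2), with no comparison during the trial attached. The design, sample size, statistics and adverse-event sections name no interim comparison, monitoring body or trial-level stopping criterion.

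**The concern.** The protocol's own account makes worse function in the intensive arm a live possibility, yet the size is justified only by a gain and nobody is charged with comparing the arms while patients are being enrolled.

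The stated safety routes fit this risk poorly. In the two adverse trials the reported excess was in 3-month function, without a significant difference in sICH or in the mortality measure given. SAE reports mainly bring in deaths and serious bleeds, one at a time. With 35% independence expected in controls, about 65% of control patients will be dependent or dead at 90 days anyway. A rise to 75% in the other arm does not show in individual cases; it shows only when the arms are set side by side. At stake is how many further patients are given the intensive target if it does worsen function.

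**Working it through.** **1. The plan's own figure.** With p1 = 0.35, p2 = 0.45, p̄ = 0.40, two-sided α = 0.05 and 80% power:

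n = [1.960·√(2·0.40·0.60) + 0.842·√(0.35·0.65 + 0.45·0.55)]² / 0.10² = 375.6, so 376 per group.

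This matches Section 5. Less 20% dropout, 455 per group leaves 455 × 0.8 = 364 evaluable.

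**2. Without a look.** Suppose the true rates are 35% and 25% (an assumption; the protocol gives no harm rate). With 364 per group, the standard error under the null is s0 = √(2·0.30·0.70/364) = 0.0340 and under the alternative s1 = √((0.2275 + 0.1875)/364) = 0.0338. The chance that the final test shows harm is Φ((0.10 − 1.96·0.0340)/0.0338) ≈ 84%, but only after about 455 patients have been assigned the intensive target.

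**3. One harm look.** Trigger: 455 patients with 90-day data, about 227 per group. Endpoint: mRS ≤2. A signal occurs if the pooled z is ≤ −b. With δ = pT − pC,

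P(signal) = Φ((−b·s0 − δ)/s1).

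For −10 points, s0 = √(2·0.30·0.70/227) = 0.0430 and s1 = √(0.415/227) = 0.0428. With b = 1.96 this is Φ((0.10 − 0.0843)/0.0428) = Φ(0.37) ≈ 64%.

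| True rate, intensive arm (control 35%) | b = 1.96 | b = 3 |
|---|---|---|
| 25% (−10) | 64% | 25% |
| 27% (−8) | 45% | 12% |
| 30% (−5) | 21% | 3% |
| 35% (no effect) | 2.5% | about 0.1% |
| 45% (+10) | about 0.002% | negligible |

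Simulation agrees with these values. If the look is instead taken on half the enrolled patients less 20% dropout (182 per group), detection at −10 points is about 55%, so the conclusion does not hinge on the exact timing.

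**4. Effect on the benefit test.** A harm-only look offers no extra chance to claim benefit, so it cannot raise that error rate. Simulated power at 45% versus 35% with 376 per group is 79.8% whether or not every harm signal is acted on.

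**5. Three endpoints.** The 2.5% holds for mRS alone. If p<0.025 is applied separately to mRS, mortality and sICH, the upper bound on a false signal is 3 × 2.5% = 7.5%. Simulation under no effect gives about 7%, assuming mortality of 10–20%, sICH of 4–8% and half of sICH fatal. If mRS truly improves by 10 points and the other two are unchanged, a false signal still occurs in about 5%. With |z|>3 on each endpoint, the figure under no effect is about 0.4%.

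**6. What a look can save.** If 455 with data are 80% of those reaching 90 days, about 455/0.8 = 569 have been enrolled, leaving at most 910 − 569 = 341, of whom about 170 are in the intensive arm. With no dropout, at most 455 remain, about 227 intensive. At −10 points that is at most 17 to 23 losses of independence, before subtracting patients enrolled during the 90-day lag. The protocol gives no accrual rate, so that deduction cannot be computed.

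**The case against.** **The protocol is silent; it does not rule a look out.** A reader might infer that a trial without interim analysis has been laid down. Section 5 gives a sample size and does not say so. Boundaries and timing often sit in an analysis plan or a monitoring charter, and neither is at hand. This stands for the details. It is weaker for whether anyone compares the arms at all, which is a design and safety matter that a protocol normally settles.

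**Harm would not be wholly invisible.** A reader might infer that an adverse effect stays unseen until everyone has been treated. The documents do not support that: every death is an SAE and reaches the sponsor and ethics committee within 24 hours, only the endpoint assessment is described as blinded, and the statistical unit in Section 15 holds a copy of the CRFs. The means to compare exist. What is missing is a stated duty to do so, and SAE reports do not give the distribution of 90-day mRS by arm.

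**The evidence is mixed.** A reader might infer that the intensive target is already known to be harmful here. The adverse trial with the same contrast ran longer and in mixed etiologies, and two cited trials did not show harm, although neither is reported with a <120 mmHg target. Which target is right is not judged here.

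**A look is limited and not free.** It misses most trials with a 5-point harm and about a third with a 10-point harm, and an unallocated boundary on three endpoints costs about 7% false signals. This stands and shapes the recommendation.

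**Conclusion.** The point holds in this form: the protocol adopts a contrast that it reports as worsening function in another setting, sizes the trial only for improvement, and states no by-arm comparison during the trial. Its single-patient provisions are poorly suited to showing the kind of harm it describes.

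One look on mRS with about 227 per group would flag a 10-point harm in about 64% of trials and a 5-point harm in about 21%. These figures rest on the 35% control rate and on assumed harm sizes. The three-endpoint figures also rest on assumed mortality and sICH rates. This is an inexpensive safety improvement that should be made. It is not an error that invalidates the final analysis.

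**What to change.** In Section 5, with a cross-reference in 13.4, state the following.

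- One confidential, harm-only, non-binding review by arm when about 455 patients have 90-day data. The statistical unit named in Section 15 could prepare it for people outside the investigator team, for example the ethics committee that already receives the SAEs.
- One clear boundary rule: either 90-day mRS ≤2 as the single boundary endpoint (for example one-sided p<0.025 against the intensive arm), with mortality and sICH shown descriptively; or one overall boundary allocated across the three (an equal split of 0.025 is about 0.0083 each); or a strict boundary such as |z|>3 on each.
- No early claim of benefit is possible, so the final two-sided 0.05 test is unchanged.

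If such a review already exists in another document, the protocol should say so and point to it.

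**Cost.** A protocol amendment, one closed tabulation and a short review, with no extra patients and no alpha spent on benefit. The false-harm-signal risk under no effect is 2.5% for mRS alone at 0.025, or about 0.4% with |z|>3 on all three endpoints. The stricter boundary detects less: on mRS, about 25% instead of 64% at −10 points.

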7.1. Intensive blood pressure control group (experimental group)

The target blood pressure is <120 mmHg within 1 hour after randomization, and this level should be maintained for at least 48 hours. Intravenous antihypertensive treatment should begin immediately after randomization. A systolic pressure of 100 mmHg is the threshold for discontinuing both antihypertensive and vasopressor therapy. Oral antihypertensive agents may be used once blood pressure stabilizes. Care should be taken to avoid the occurrence of hypotension.

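### One stated block size of 10, with treating staff aware of each arm, lets some end-of-block allocations be deduced before the patient is enrolled (minor)

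*Protocol*

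**What the plan says.** Protocol Section 5, in the paragraph after the sample size, states: "Randomization will be performed using block randomization with block size of 10 (with at least 10 participants per center". It continues: "For practical implementation, each center will be allocated a block", with the example that "if Center 1 plans to enroll 20 participants, blocks 1-2 will be allocated". It then adds, conditionally: "If stratification variables are used, randomization will be performed within each stratum".

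Section 6 settles that condition: "Stratified block randomization will be used, with stratification by study center and intravenous thrombolysis". The process is run through an app. The protocol nowhere says that block sizes vary or that the size is kept from sites.

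On blinding, Section 3 says: "The study employs a multicenter, prospective, randomized, endpoint-blinded, parallel-controlled trial design". Treating staff cannot be blind to the arm. In the experimental arm (Section 7.1), "Intravenous antihypertensive treatment should begin immediately after randomization", towards a systolic target below 120 mmHg. In the control arm (Section 7.2) the target is 140–180 mmHg, with a different rule for starting intravenous drugs.

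**The concern.** Concealment means that whoever decides on entry cannot know the next allocation. With a known fixed block size and visible past arms, that fails towards the end of a block: after five of one arm, all the remaining places must go to the other. An app hides the list but cannot prevent this deduction.

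Staff who know the next arm can influence whether the next patient enters. Two steps leave room for it: whether consent is sought (Section 4.1), and the closing exclusion in Section 4.2, which rests on the investigator's judgement of suitability and which its examples narrow but do not close. Section 1 reports worse functional outcomes with more intensive control in two earlier trials, so some investigators may hold a view about the arms. Blinded endpoint assessment does not correct selective entry, because the selection happens before randomisation.

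There is also an editorial point, which is not a contradiction. The conditional sentence on stratification in Section 5 is out of date given Section 6, and the two-block example ignores the thrombolysis strata.

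**Working it through.** **Inputs from the protocol.** Block size 10, 1:1 allocation (five per arm in each block), at least 10 patients per centre and 910 patients in total (Section 5); lists by centre and thrombolysis (Section 6).

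**Assumptions, because the protocol gives no figures.** Thrombolysis share 30%, 40% or 50%; every centre enrols the same number N = 10, 20 or 40. Ten is the stated minimum and 20 is the size in the protocol's own example.

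**One completed block.** Place k is certain if one arm has already used its five places:

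P(place k certain) = 2 × C(k−1, 5) / C(10, 5), with C(10, 5) = 252.

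| k | 1–5 | 6 | 7 | 8 | 9 | 10 |
|---|---|---|---|---|---|---|
| P | 0 | 0.008 | 0.048 | 0.167 | 0.444 | 1.000 |

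The sum is 1.667 per block, or 16.7% of allocations. Enumerating all 252 balanced blocks gives the same mean. At least two places are certain in 44.4% of blocks.

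**The whole trial.** For a list of n patients, let c(n) = 1.667 × floor(n/10) plus the sum of P over the first (n mod 10) places. A centre of N patients has two lists, of A and N − A patients, with A ~ Binomial(N, share). The expected number of certain allocations per centre is E[c(A) + c(N − A)], and there are 910/N centres.

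| N per centre | Centres | Per centre, share 30% / 40% / 50% | Of 910 patients |
|---|---|---|---|
| 10 | 91 | 0.197 / 0.085 / 0.052 | 18.0 / 7.7 / 4.7 |
| 20 | 45.5 | 1.824 / 2.077 / 2.236 | 83.0 / 94.5 / 101.8 |
| 40 | 22.75 | 5.404 / 5.286 / 5.433 | 122.9 / 120.3 / 123.6 |

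The formula treats the two lists alike, so shares of 50% to 70% give the same range. The upper bound is 91 × 1.667 = 152 of 910, reached if every block is filled.

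**Varying block sizes.** These were simulated with an observer who knows the set of sizes and every past allocation, and who updates exactly by Bayes' rule. The entries are certain allocations of 910, at shares 30% / 50%.

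| N per centre | Fixed 10 (formula) | 8/10/12 | 4/6/8 |
|---|---|---|---|
| 10 | 18.0 / 4.7 | 0.6 / 0.0 | 12.9 / 7.8 |
| 20 | 83.0 / 101.8 | 13.2 / 12.1 | 19.1 / 19.9 |
| 40 | 122.9 / 123.6 | 15.8 / 14.3 | 22.9 / 20.8 |

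The same simulation with fixed 10 gave 18.4 / 4.4, 83.9 / 103.4 and 125.0 / 122.0, in line with the formula.

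**General guessing.** For a completed block of size 2m, always guessing the arm that is behind is right in a fraction [m + (4^m / C(2m, m) − 1)/2] / (2m). For m = 5 this is [5 + (1024/252 − 1)/2]/10 = 0.653. Weighted by patients, 8/10/12 also gives 0.653 and 4/6/8 gives 0.681. In the partly filled lists expected here, the best-guess rates over the three centre sizes are lower: about 57%–64% for fixed 10, the same for 8/10/12, and 63%–67% for 4/6/8.

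**The case against.** A fixed block of 10 is a conventional choice and not a small block, and nothing is certain before the sixth place. Exploiting it needs staff who know the size, who keep a complete count for each thrombolysis stratum, and who have a discretionary step left once they know the next arm. Most entry criteria are objective: reperfusion grade, absence of stenosis, two systolic readings of at least 140 mmHg, ASPECTS and NIHSS. The protocol does not place consent in time beyond before randomisation, so its use as a selection step is possible but not shown. The size rests on assumed centre sizes and thrombolysis shares, and the range from 0.5% to 13.6% of patients is wide. Varying block sizes also leave the general guess rate unchanged.

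Most of this stands, and it is why the point is minor. It does not remove it. The protocol states the block size in a document that sites hold, so this is not a detail left for later. Thrombolysis details are a baseline item in the Section 12 schedule, so staff can tell which list the next patient belongs to. Allocations known with certainty are a different matter from a modest edge in guessing, and the certain ones can be nearly eliminated at little cost.

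**Conclusion.** The concern holds as a minor weakness in allocation concealment. With a known fixed block of 10, 16.7% of allocations in completed blocks can be deduced in advance. Across the trial this is about 5–18 of 910 patients (0.5%–2.0%) if every centre enrols 10, 83–102 (9.1%–11.2%) at 20, and 120–124 (13.2%–13.6%) at 40, with 152 as the ceiling. These counts assume equal centre sizes, a 30%–50% thrombolysis share, and staff who know the size and track every allocation in the stratum. They count what could be deduced. They do not show that selection would occur or that the treatment estimate would shift.

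**What to change.** Use permuted blocks within centre-by-thrombolysis strata, with block sizes varying at random (for example 8/10/12), generated in the randomisation app, withheld from sites and not stated in the protocol. In the same edit, delete from Section 5 the fixed size of 10, the two-block example and the conditional sentence on stratification, so that Section 6 alone governs.

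A 4/6/8 mix is a weaker choice. It is easier to guess, and at 10 per centre with a 50% share it leaves about 8 certain allocations against about 5 under fixed 10.

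The cost is one app setting and a short protocol edit. If enrolment has begun, apply the change to new blocks only. There are two limits. The change removes nearly all certain allocations but leaves general guessing as it was. An unfilled block of 12 can also be out of balance by up to 6 patients, against 5 for a block of 10.
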